	
non-atopic disease within 90 days preceding Initial Dose Escalation Day (IDED) or at any time after the IDED
 
 • Use of beta-blockers (oral) • Pregnancy or lactation • Allergy to oat • History of severe anaphylaxis to cashew or shrimp with symptoms including hypotension requiring fluid resuscitation and/or the need for mechanical ventilation within the last year • Use of investigational drugs within 12 weeks of participation • Past or current medical problems or findings from physical assessment or laboratory testing that are not listed above, which, in the opinion of the investigator, may pose additional risks from participation in the study, may interfere with the participant’s ability to comply with study requirements or that may impact the quality or interpretation of the data obtained from the study

Study Stopping Rules
	
During the study, if the investigator or the NIAID Medical Officer discovers conditions that indicate that the study should be discontinued, an appropriate procedure for stopping the study pending DSMB review will be instituted.
 
If any of the stopping rules listed below are met, study enrollment will be suspended, the Initial dose day will be suspended, dose escalation during Build-up will be stopped, and all enrolled participants will remain on their current dose pending expedited review of all pertinent data by the Data Safety Monitoring Board:
 
 • Any death related to cashew or shrimp OIT dosing • More than 3 cases of CoFAR Grade 4 AE related to food allergen dosing or to oral food challenge. • More than 3 participants require more than 2 injections of epinephrine during a single dosing of cashew or shrimp OIT investigational product • More than 3 of the following events: 
 ○ Severe adverse event, other than anaphylaxis, related to investigational product ○ Eosinophilic esophagitis

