12.8.2 DSMB Review

12.8.2.1 Planned DSMB Reviews

The Data and Safety Monitoring Board (DSMB) shall review safety data at least yearly during planned DSMB Data Review Meetings. Data for the planned safety reviews will include, at a minimum, a listing of all reported AEs and SAEs.

The DSMB will be informed of an Expedited Safety Report in a timely manner.

12.8.2.2 *Ad hoc* DSMB Reviews

In addition to the pre-scheduled data reviews and planned safety monitoring, the DSMB may be called upon for *ad hoc* reviews. The DSMB will review any event that potentially impacts safety at the request of the protocol chair or DAIT/NIAID. In addition, the following events will trigger an *ad hoc* comprehensive DSMB Safety Review:

- Any death related to food allergen OIT dosing
- One case of severe and prolonged anaphylaxis that does not respond to 3 doses of epinephrine, or that includes intubation and that is related to food allergen dosing or to oral food challenge.
- More than 2 cases of hypotension related to food allergen dosing or to oral food challenge.
- More than 3 of either of the following events:
 - Severe adverse event, other than anaphylaxis, related to investigational product or
 - Eosinophilic esophagitis with synchronous clinical symptoms and confirmatory biopsy findings

After review of the data, the DSMB will make recommendations regarding study conduct and/or continuation.

12.8.2.2.1 Temporary Suspension of enrollment/drug dosing or both for *ad hoc* DSMB Safety Review

A temporary halt in enrollment, initial dose days and drug up dosing *will* be implemented if an *ad hoc* DSMB safety review is required per the criteria outlined in section 12.8.2.2. above.

In the event of a study halt for DSMB review, subjects in the screening phase will continue to undergo screening procedures unless the review was triggered by events related to screening. Subjects already receiving therapy will remain on study treatment at their current tolerated dose.

Based on the outcome of the DSMB review, the consent and/or assent forms may be revised. Upon approval of these revisions by the IRB, all subjects who have previously provided informed consent for the study and are affected by the new information will be re-consented.

13. Statistical Considerations and Analytical Plan

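### The synopsis and section 12.8.2.2 attach the same study-wide halt to different trigger lists and event counts, and nothing says whether both apply.

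*Combined protocol and SAP*

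**What the plan says.** **Synopsis, Study Stopping Rules.** The consequence is stated first: "If any of the stopping rules listed below are met, study enrollment will be suspended". Initial dose days are also suspended, escalation stops, and participants stay on their current dose until the DSMB has reviewed the data. Besides any related death, the triggers are:

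- a rule on the broad Grade 4 class, which counts challenge reactions as well as dosing reactions: "More than 3 cases of CoFAR Grade 4 AE related to food allergen dosing or to oral food challenge";
- a rule on repeated rescue treatment, which counts people rather than events: "More than 3 participants require more than 2 injections of epinephrine during a single dosing of cashew or shrimp OIT investigational product";
- a last item, introduced by "More than 3 of the following events", that takes in severe related adverse events other than anaphylaxis, and eosinophilic esophagitis (EoE) with no further qualification.

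**Sections 12.8.2.2 and 12.8.2.2.1.** Meeting a listed criterion triggers an ad hoc DSMB review, and such a review brings a temporary halt to enrollment, initial dose days and updosing, with treated participants held at their current tolerated dose. Besides any related death, the triggers are:

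- a single-case rule on anaphylaxis, "One case of severe and prolonged anaphylaxis that does not respond to 3 doses of epinephrine, or that includes intubation", whether it arises from a dose or from a challenge;
- a separate rule on low blood pressure: "More than 2 cases of hypotension related to food allergen dosing or to oral food challenge";
- a last item, introduced by "More than 3 of either of the following events", whose first part is "Severe adverse event, other than anaphylaxis, related to investigational product" and whose second part is EoE that is both symptomatic and biopsy-confirmed.

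**Section 11.5**, which has the same title as the synopsis entry, gives no list and refers the reader to 12.8.2.2 alone.

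**Section 12.3.1, Table 4** places laryngeal edema, respiratory compromise needing mechanical support, and low blood pressure with end-organ symptoms in CoFAR Grade 4. **Section 12.2.1** states that food-challenge material is not study drug.

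**The concern.** The two lists overlap in the events they cover but not in the counts at which they act, and each contains triggers that the other lacks. The synopsis is therefore not a shortened form of the body text, and neither list is uniformly stricter. Someone who follows the cross-reference in 11.5 applies one set of rules. Someone who works from the synopsis applies another.

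What is at stake is when the study halts automatically. Planned DSMB review is only at least yearly (12.8.2.1), and section 13.5.2 plans no interim analysis of safety data. The trigger list is thus the main pre-specified study-level halt between planned meetings, and it should give one answer on any given set of events.

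**Working it through.** The plan gives no operating characteristic for either list, so there is no figure to reproduce. The check sets the lists side by side and applies each to the same hypothetical data.

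**Trigger by trigger**, with the last item of each list split in two, giving five triggers per list:

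| Event | Synopsis | 12.8.2.2 | Same decision? |
|---|---|---|---|
| Related death | 1st | 1st | Yes |
| Severe related AE, not anaphylaxis, counted alone | 4th | 4th | Yes |
| EoE | 4th, unqualified | 4th, with symptoms and biopsy | Not as worded |
| Any CoFAR Grade 4, dosing or challenge | 4th case | Not listed | No |
| More than 2 epinephrine injections in one OIT dosing | 4th participant | Not listed | No |
| Hypotension | Not listed; symptomatic cases count as Grade 4 | 3rd case | No |
| Severe, prolonged anaphylaxis, refractory to 3 doses or intubated | Not listed; intubated cases count as Grade 4 | 1st case | No |

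On the literal wording, 2 of 5 triggers in each list give the same decision.

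**Four scenarios**

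- **A.** Three symptomatic hypotension cases and no other Grade 4 event. Synopsis: 3 is not more than 3, so no trigger is met. 12.8.2.2: 3 is more than 2, so the study halts.
- **B.** One severe, prolonged anaphylaxis with intubation. Synopsis: one Grade 4 case, so no trigger is met. 12.8.2.2: one case suffices, so the study halts.
- **C.** Four Grade 4 reactions during food challenges (for example laryngeal edema), without hypotension, intubation or failure of 3 epinephrine doses. Synopsis: 4 is more than 3, so the study halts. 12.8.2.2: no listed trigger, because its severe-event item covers only the investigational product and 12.2.1 says challenge material is not study drug.
- **D.** Four participants with anaphylaxis to OIT, each given 3 injections in one dosing, who respond without hypotension or intubation. Synopsis: 4 participants is more than 3, and 3 injections is more than 2, so the study halts. 12.8.2.2: no listed trigger, because its severe-event item excludes anaphylaxis and its anaphylaxis item requires non-response or intubation.

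A and B halt the study only under the body list. C and D halt it only under the synopsis list.

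**Counting.** The synopsis wording of the last item can be read as pooling severe events with EoE, while 12.8.2.2 suggests separate counts. Two of each would be 2 + 2 = 4, which exceeds 3 if pooled but not if counted separately. This ambiguity is not used in the tally above.

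**Illustration of scale, on assumed rates.** Take 72 participants, at most one event each, all events symptomatic hypotension and no other Grade 4 event. The binomial probability of reaching the 3rd case (12.8.2.2) against the 4th (synopsis) is:

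| Assumed rate per participant | At least 3 | At least 4 |
|---|---|---|
| 1% | 3.6% | 0.6% |
| 2% | 17.5% | 5.7% |
| 5% | 70.5% | 48.8% |

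The documents do not give these rates, and the contradiction does not depend on them.

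**The case against.** The strongest reply is that the lists do not conflict. Each is worded as sufficient, neither says that only its own triggers count, and a literal reader could apply both, so that A to D would all halt the study. A lower count for named severe events can sensibly sit beside a higher count for the broad Grade 4 class. This reading is possible, but the protocol never states it. Section 12.8.2.2.1 ties the halt to the criteria in 12.8.2.2, and 11.5 cites only that section, so the protocol's own cross-reference leads away from the synopsis triggers.

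Second, EoE is described as symptomatic and biopsy-documented in the discontinuation rules of the synopsis and section 6.5. If that definition carries over to the synopsis stopping list, agreement rises to 3 of 5. Those rules concern individual discontinuation, however, and the study-level item as written has no qualifier.

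Third, scenario C may be rare. Section 5.2 anticipates life-threatening anaphylaxis during food challenges at below 0.1%. Assume one food each, full attendance and challenges at screening and weeks 52 and 58, which gives 72 × 3 = 216 active challenges. Taking 0.1% as a per-challenge Grade 4 rate, the binomial chance of at least 4 is about 0.007%. It is 2.4% at an assumed 0.5% and 17% at 1%. This limits the likely frequency of C, but says nothing about OIT dosing reactions or about A, B and D.

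Fourth, other safeguards exist: individual stopping rules (synopsis, 11.2, Appendix 2), including the synopsis rule that covers food challenges; 24-hour SAE reporting; discretionary stopping; DSMB review on request; and conduct at a single site. These reduce the risk and deserve credit. None of them sets the count at which the study halts.

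**Conclusion.** The concern holds, and the text is wrong as written. The same halt is attached to two lists that can give opposite decisions on the same events. The differences run in both directions: symptomatic hypotension at the 3rd case against the 4th Grade 4 case; severe, prolonged anaphylaxis with intubation at the 1st case against the 4th Grade 4 case; and two patterns of four events that halt the study under the synopsis but match nothing in 12.8.2.2.

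This conclusion rests on the wording of the two lists and on Table 4, not on any assumed event rate. One qualification is needed: 12.8.2.2 counts hypotension without defining it, whereas Grade 4 requires end-organ symptoms. The categories therefore overlap rather than coincide, and scenario A is restricted to symptomatic cases for that reason. The point should be fixed because it concerns a safety halt. No view is taken on which threshold is right.

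**What to change.** Reconcile the passages into one governing trigger table in 12.8.2.2, and cite it or repeat it verbatim in the synopsis and 11.5. The table should cover Grade 4 reactions, hypotension, anaphylaxis with intubation or epinephrine failure, repeated epinephrine use, severe non-anaphylaxis events and EoE, and should retain the related-death trigger on which the lists already agree. For each event, state the grading scale, the case definition, whether food-challenge reactions count, and whether counts are pooled or separate. The sponsor's medical officer and the DSMB decide the thresholds.

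The cost is one protocol amendment with their sign-off and the IRB approval that section 16.1 requires. No new data collection is needed.

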EOS	End Of Study
FA	Food Allergen
FDA	Food and Drug Administration

GCP	Good Clinical Practice
ICH	International Conference on Harmonization
IDD	Initial dose day
IEC	Institutional Ethics Committee
IMM	Independent Medical Monitor
IND	Investigational New Drug
IRB	Institutional Review Board
MOP	Manual of Procedures
NIAID	National Institute of Allergy and Infectious Diseases
PC	Protocol Chair
PI	Principal Investigator
SACCC	Statistical and Clinical Coordinating Center
SAE	Serious Adverse Event
SAP	Statistical Analysis Plan
SAR	Suspected Adverse Reaction
SMC	Safety Monitoring Committee
SNP-CRU	Sean N Parker-Clinical Research Unit
SOP	Standard Operating Procedure
SU	Sustained Unresponsiveness
SUSAR	Serious Unexpected Suspected Adverse Reaction

Study Definitions Page

Desensitization	Participants that pass their food challenge with no or mild objective reactions to up to a cumulative 2043 mg of the food allergen in their OIT at end of maintenance phase (week 52) will be considered desensitized.
Desensitization Failure	Participants who tolerate OIT but do not tolerate at least 2043 mg of food allergen at week 52.
Double blind placebo controlled food challenge	A graded challenge of suspect allergenic or placebo food product where neither the patient nor the supervising physician is aware of which product the patient is ingesting.
Independent Medical Monitor	This a physician experienced in clinical trials who is administratively independent of the investigative team. They serve as a contact who is able to review the situation at the site for the DAIT team in the event of any occurrence of concern.
Lost to Follow-up	Lost to follow-up refers to patients who at one point in time were actively participating in a clinical research trial but have become lost (either by error in a computer tracking system or by being unreachable) at the point of follow-up in the trial.
Maintenance Failure	Participants who cannot tolerate 1000 mg but are not withdrawn due to unacceptable side effects.
NAEPP EPR-3	The EPR 3 Guidelines on Asthma was developed by an expert panel commissioned by the National Asthma Education and Prevention Program (NAEPP) Coordinating Committee (CC), coordinated by the National Heart, Lung, and Blood Institute (NHLBI) of the National Institutes of Health. Using the 1997 EPR 2 guidelines and the 2004 update of EPR 2 as the framework, the expert panel organized the literature review and final guidelines report around four essential components of asthma care, namely: assessment and monitoring, patient education, control of factors contributing to asthma severity, and pharmacologic treatment. Subtopics were developed for each of these four broad categories. (https://www.nhlbi.nih.gov/health-topics/guidelines-for-diagnosis-management-of-asthma)
Natural tolerance	Naturally tolerant individuals are defined as individuals who had clinically diagnosed food allergies by oral food challenge (OFC) who then lost those food allergies over time without treatment and have a verified negative OFC for that food allergen.
Non-adherence	Non-adherence with home OIT dosing protocol (excessive missed days more than 20 days) without consulting with study staff would be a safety issue warranting discontinuation
PRACTALL guidelines	The PRACTALL program is a common initiative of EAACI and the American Academy of Allergy, Asthma and Immunology. It focuses on practical aspects of allergy to deliver updated and evidence-based recommendations for clinicians. DOI: https://doi.org/10.1016/j.jaci.2012.10.017

Principal Investigator	A person responsible and accountable for conducting the clinical trial and for the rights, health and welfare of the subjects in the trial. The principle investigator assumes full responsibility for the evaluation of human subjects, and for the integrity of the research data and results.
Protocol Mandated Procedures	Procedures mandatory per protocol.
Site Principal Investigator	Site Principal Investigator is the Principal Investigator at the lead research site and has responsibility over the conduct of a clinical study at that site.
Site Study Coordinator	A Clinical Research Coordinator (CRC) is a person responsible for conducting clinical trials using good clinical practice (GCP) under the auspices of a Principal Investigator (PI).
Study Termination	Permanent cessation of all research activities.
Study Therapy	Specific intervention according to the research plan or protocol created by the investigator.
Sustained unresponsiveness	Sustained unresponsiveness corresponds to the effects of OIT and will be defined as a participant's passing a Double-blind Placebo-controlled Food challenge (DBPCFC) with no or mild objective reaction to up to a cumulative 2043 mg of the FA allergen in their OIT at week 58.
Sustained unresponsiveness Failure	Participants who tolerate at least 2043 mg cumulative protein at the week 52 DBPCFC with no or mild objective reactions, but who can no longer tolerate at least this dose at the week 58 DBPCFC
T cell epitopes	A peptide sequence that can bind to a specific T cell receptor when presented in the context of MHC
Tetramers	A group of 4 engineered defined, soluble MHC/peptide multimers capable of engaging more than one copy of the TCR on the surface of a T cell to identify antigen-specific T cells by flow cytometry, even those present at low frequencies in fresh populations of lymphocytes sampled directly ex vivo .
Tolerance (immune)	Long term sustained unresponsiveness: this is a similar definition as sustained unresponsiveness but instead of week 58, will be determined in long term follow up under a different protocol at 5 years after study start for each participant.
Treatment Failure	Treatment failures will be defined as those participants who withdraw or are withdrawn due to unacceptable side effects of OIT
Withdrawal from Therapy	Therapy is stopped as directed per protocol, participant's decision or per study withdrawal criteria.

1. Background and Rationale

1.1. Background and Scientific Rationale

Food allergy (FA) is now recognized to be a major health concern affecting about 8% of the US population and costing the healthcare system and families about \$24.8 billion per year. About 40% of children with food allergy have experienced a severe, life-threatening allergic reaction, and 30% report allergies to multiple foods. There is an unmet need for new therapies in food allergy as many patients with food allergies are at risk for accidental reactions, especially those with cashew, and shrimp allergies. Current OIT remains associated with refractory vs. successfully treated populations due to a number of cellular and molecular mechanisms, with a predominance of cellular changes occurring in food allergen-specific (FS) T cells.¹⁻⁴ There is an unmet need for new therapies in FA, since many patients in OIT trials continue to have side effects that can hinder their compliance and the overall efficacy of OIT. Current OIT is not universally effective. A significant portion of food allergic patients fall into the refractory or fail-to-treat populations, likely due to variability of cellular and molecular endotypes and clinical phenotypes.^{5,6} To address these challenges and to test the ability to desensitize to cashew, or shrimp, we propose a Phase 2 clinical trial using OIT for cashew or shrimp allergies in participants with proven allergies to either cashew or shrimp, respectively, to link clinical outcomes with food allergen-specific T cell studies and epitope discovery and validation. For our clinical research hypotheses, we will test the safety and efficacy of cashew or shrimp allergen desensitization using validated and standardized endpoints. For our mechanistic hypotheses, we hypothesize that T cell epitopes and TCR repertoire/targeted RNA-Seq in participants achieving clinical success at 52 weeks will change significantly as compared to baseline. As a corollary, we hypothesize that T cell epitopes and TCR repertoire/targeted RNA-Seq in participants achieving clinical success at desensitization vs. sustained unresponsiveness (SU) will differ as compared to baseline.

1.2. Rationale for Selection of Investigational Product or Intervention

We have designed the primary endpoint based on preliminary mechanistic understandings of T cell modifications over time during immunotherapy. When first activated, T-cells initially start making Th2 products like IL4 and IL13, but over the course of therapy they start making more interferon gamma and start expressing less CD28 so that they appear more anergic (Ryan et al. PNAS 2016; Syed, et al. JACI 2014; Pellerin, et al. JACI 2018). The hypothesis would be to expect a change of 20% in the T cell population to shift within 52 weeks toward this activated allergen-specific subset that makes interferon gamma and is more anergic. Exploratory endpoints will include the changes in the transcriptomes and phenotypes of tetramer+ T cells from baseline to 52 weeks, 58 weeks and to 64 weeks.

Our and others' community-based participatory research⁷⁻⁹ show that many patients and families would prefer to be desensitized to a low dose of FA protein (300mg) to avoid worry about accidentally eating a contaminated food, while others would prefer to safely ingest a larger dose of FA protein (1,000 mg or more) to be able to try certain foods containing the FA; therefore, we have proposed using these two quantities in our clinical study as the treatment dose (1000 mg) and the desensitization threshold (2,043 mg). There are several lines of evidence (Jones, et al. AAAAI, 2018, Phase 3 results of PALISADES study and Andorf, et al. AACI 2017

<https://www.ncbi.nlm.nih.gov/pmc/articles/PMC5738818/>) demonstrating that 300 mg of maintenance of each food allergen protein will allow some protection in the majority of participants to at least 1000 mg of each food allergen protein during a standardized food challenge. However, recent data has shown that maintenance at higher levels (i.e. 1000 mg) would afford protection to higher levels of accidental ingestion (for shrimp, since the average shrimp is approximately 8g, we prefer to propose 1000 mg maintenance in this study) and perhaps could improve SU outcomes.

The data from previous and our current OIT Phase 1 and 2 studies indicate that a clinically meaningful level of desensitization can be achieved after up dosing. Accordingly, our pilot phase 2 clinical trial proposes to achieve maintenance dosing by week 52 and to test desensitization with DBPCFCs at week 52 and sustained unresponsiveness with DBPCFCs at weeks 58 and 64. which should provide sufficient time to test efficacy and assess trends in safety.

